12.1 Definitions

12.1.1 Adverse Event

Adverse event (AE) means any untoward medical occurrence in a patient or clinical trial patient associated with the use of a drug in humans, whether or not considered drug related. An AE can be:

- any unfavorable and unintended sign (including an abnormal laboratory finding, for example), symptom or disease temporally associated with the use of a medicinal product, whether or not considered related to the medicinal product.
- any occurrence that is new in onset or aggravated in severity or frequency from the baseline condition, or abnormal results of diagnostic procedures, including laboratory test abnormalities.

12.1.2 Adverse Drug Reaction

Adverse drug reaction (ADR) is a noxious and unintended response to the medicinal product related to any dose. As used herein, the phrase “response to a medicinal product” means that a causal relationship between a medicinal product and an AE is at least a reasonable possibility.

12.1.3 Adverse Event of Special Interest

An adverse event of special interest (AESI) is an event of scientific and medical interest or concern to the Sponsor’s product or program, for which ongoing monitoring and rapid communication to the Sponsor could be appropriate. It may be a serious or non-serious AE, which may require further investigation in order to characterize and understand it.

12.1.4 Serious Adverse Event

A serious AE (SAE) is any AE that results in any of the following outcomes:

- Death
- Life-threatening (immediate risk of death)

- Inpatient hospitalization for longer than 24 hours or prolongation of existing hospitalization (even if the event is Grade 1)
- Persistent or significant disability or incapacity
- Congenital anomaly/birth defect
- Important medical events

12.1.5 Attribution/Assessment of Causality

Attribution/Assessment of Causality is a determination that describes the relationship or association of the study product with an AE.

This assessment of causality or relationship of AEs to the study drug is provided by the Investigator and is determined by 1) temporal relationship of the event to the administration of study drug; 2) whether an alternative etiology has been identified, and 3) biological plausibility. Causality must be assessed separately for each study drug.

Causality assessments that are considered **not related** to study drug:

- *None*: The event is related to an etiology other than the study drug (the alternative etiology should be documented in the patient's medical record).
- *Unlikely*: The event is unlikely to be related to the study drug and likely to be related to factors other than study drug. An alternative explanation is more likely (e.g., concomitant drugs, concomitant disease), or the relationship in time suggests that a causal relationship is unlikely.

If an SAE is considered "unlikely" or "unrelated" to study drug, the Investigator should offer his/her clinical opinion as to what factor(s), agent(s), or process(es) were the likely causative mechanism for the event.

Causality assessments that are considered **related** to study drug:

- *Possible*: There is an association between the event and the administration of the study drug and there is a plausible mechanism for the event to be related to study drug; but there may also be alternative etiology, such as characteristics of the patient's clinical status or underlying disease.
- *Probable*: There is an association between the event and the administration of study drug; there is a plausible mechanism for the event to be related to the study drug and the event could not be reasonably explained by known characteristics of the patient's clinical status or an alternative etiology is not apparent.

- *Definite*: There is an association between the event and the administration of study drug; there is a plausible mechanism for the event to be related to the study drug, causes other than the study drug are ruled out, and/or the event re-appeared on re-exposure to the study drug.

12.1.6 Severity Criteria

Assessment of severity grade will be made using the NCI-CTCAE Version 5.0.

For events not contained in CTCAE, the Investigator may assign intensity according to the following generic CTCAE grading scale:

- Grade 1 = Mild; asymptomatic or mild symptoms, clinical or diagnostic observations only; intervention not indicated.
- Grade 2 = Moderate; minimal, local or noninvasive intervention indicated; limiting age-appropriate instrumental activities of daily living (ADL).
- Grade 3 = Severe or medically significant but not immediately life-threatening; hospitalization or prolongation of hospitalization indicated; disabling; limiting self-care ADL.
- Grade 4 = Life-threatening consequences; urgent intervention indicated.
- Grade 5 = Death related to AE.

12.2 Adverse Event Collection and Documentation

12.2.1 All Adverse Events

All patients who receive at least one dose of study drug will be considered evaluable for safety. AEs will be determined based on signs, symptoms, physical examination findings, and/or laboratory test results from enrolled patients as appropriate.

All adverse events whether serious or non-serious, will be reported from the time a signed and dated informed consent form (ICF) is obtained until 30 days following the last dose of study drug or until the start of a subsequent systemic anticancer therapy, if earlier.

Both protocol-related AEs and SAEs will be collected from the time the patient has consented to study participation. AEs and SAEs reported between the time the patient signs the ICF and the administration of the first dose of study drug will be captured as concurrent medical history unless the events are attributed to protocol-specified procedures.

Disease progression or events deemed related to disease progression will be documented as an antitumor activity outcome, **not reported** as an AE; they will be collected as efficacy endpoints. **Conversely**, AEs should be reported if it is unclear if the event is due to PD.

Events attributed to protocol-specified procedures will be collected on the Adverse Event eCRFs and SAE Report Form, as appropriate.

AEs, regardless of seriousness, severity, or relationship to study drug, are documented in the source and the eCRF, including:

- duration, severity, and seriousness of each adverse event,
- the action taken with respect to the study drug(s),
- the Investigator's attribution/causality assessment,
- the outcome of the event.

Whenever possible, diagnoses should be given when signs and symptoms are due to a common etiology (e.g. cough, runny nose, sneezing, sore throat, and head congestion should be reported as "upper respiratory infection"). All treatment measures for AE management will be recorded. All non-serious AEs should be entered into the eCRFs within 10 days of study site awareness.

Clinical Laboratory Changes: Safety laboratory assessments will be evaluated by the Investigator to ensure patient safety. The Investigator is responsible for reviewing the results of all laboratory tests as they become available:

- Laboratory values that fall outside of a clinically accepted reference range or values that differ significantly from previous values must be evaluated by the Investigator for clinical significance. The Investigator may repeat the laboratory test or request additional tests to verify the results of the original laboratory tests.

A laboratory abnormality is reported as an AE if any criterion for an SAE is fulfilled, or the event is associated with an intervention including, but not limited to, discontinuation or interruption of treatment, dose reduction/delay, or required initiation of concomitant therapy. Also, any laboratory abnormality may be reported as an AE at the Investigator's discretion, based on clinical significance. Examples include abnormalities for which there are no interventions yet abnormal value(s) suggest(s) disease or organ toxicity. If clinical sequelae are associated with a laboratory abnormality, diagnosis or medical condition should be reported (e.g., renal failure, hematuria) not the laboratory abnormality (e.g., elevated creatinine, urine red blood cells [RBC] increased).

The sponsor assumes responsibility for appropriate reporting of AEs to the regulatory authorities. The sponsor will also report to the Investigator all suspected unexpected serious adverse reactions. The Investigator must report suspected unexpected serious adverse reactions to the appropriate Independent Ethics Committee/Institutional Review Board (IEC/IRB) that approved the protocol, unless otherwise required and documented by the IEC/IRB.

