4.3.1 Dose Delays

Tebotelimab Cohort

Patients who experience a Grade 2 to 4 AE that is potentially dose-limiting should have study drug held pending assessment, management, and resolution of the AE. If the AE is assessed as unrelated to study drug or does not meet DLT criteria, therapy may be restarted at the previous dose and schedule, after appropriate recovery.

Retifanlimab and Tebotelimab Cohorts

A dose delay of up to 20 days is allowed for patients experiencing AEs. In the case of abnormal troponins or N-terminal pro b-type natriuretic peptide (NT-proBNP) values, study drug must be withheld and a thorough cardiac assessment performed promptly to diagnose myocarditis or other cardiovascular diseases; the patient may resume study drugs if myocarditis is not confirmed. Refer to [Section 7](#) for specific guidance on restarting study therapy for IRR and irAEs. A dose delay of up to 20 days may also be permitted for reasons other than AEs. All procedures at the missed dosing visit should be performed and treatment reinstated as if the delay had not occurred.

Patients with infusion delays > 20 days will discontinue the study drug, complete the End of Treatment visit, and then enter the Post-treatment Follow-up Period.

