9.5 Prior and Concomitant Medications and Procedures

All concomitant medications, blood products, and procedures administered for 30 days prior to study drug administration through the End of Treatment Visit must be recorded in the source document and on the eCRF.

All prior regimens of systemic anti-cancer therapy will be documented in the medical records and on the eCRF.

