9.12 End of Treatment Visit

The end of treatment visit (EOTV) should be performed within 30 days after the patient has met study treatment discontinuation criteria, and before initiation of any subsequent anticancer therapies.

It is recognized that patients may go to other facilities for continuing care, or may elect not to return to the study site. Therefore, failure to return for an EOTV will not be considered a protocol deviation. Whenever possible all required procedures and tests should be performed, with the following exception: the EOTV tumor assessment does not need to be conducted if prior tumor assessment was performed within 28 days of the EOTV and results are available for RECIST assessments.

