12 ADVERSE EVENT REPORTING AND ASSESSMENT OF SAFETY

The safety assessment will be based on the evaluation of AEs that occur from the time of initiation of administration of study drug until 30 days following the last dose of study drug or until the start of a subsequent systemic anticancer therapy, if earlier, and will be determined based on signs, symptoms, physical examination findings, and/or laboratory test results from enrolled patients, as appropriate.

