12.2.2 Serious Adverse Events

All SAEs occurring during the study must be reported to the Sponsor. SAEs considered related to study drug may be reported at any time, even after the patient's final visit.

- **Within 24 hours** of becoming aware of an SAE, the Investigator should send the Sponsor a completed SAE Report form by email, [contact], or fax, [contact]. The SAE Report Form and Completion Guidelines, and Contact Information for Reporting SAEs, are found in the Study Procedures Manual. Upon receipt of SAE follow-up information, a follow-up SAE Report form should be submitted within 24 hours of becoming aware of the follow-up information. SAEs should be entered into the eCRFs within 5 calendar days of the site's awareness.
- SAEs related to study drug may be reported at any time, through 30 days after the last dose of study drug or until start of a subsequent anticancer therapy, if earlier.
 - In those cases in which the SAE is considered related to study drug, the study drug may be discontinued, and the patient will continue participation in the study for observational safety and analysis (except for cases where the patient is withdrawn from the study by the Investigator or withdrew the consent).
- After 30 days following the last dose of study drug administration, if an Investigator becomes aware of a SAE that s/he suspects is related to study drug, the Investigator should report the event to the Sponsor. Grade 3 or Grade 4 SAEs considered related to study drug are followed until recovery to \leq Grade 1.
- The Investigator must follow all SAEs until resolution and record the date of resolution. Resolution of an event is defined as the return to pre-treatment status or stabilization of the condition with the expectation that it will remain chronic. Unresolved SAEs must be followed until:
 - The event resolves.
 - The event stabilizes.
 - The event returns to baseline, if a baseline value/status is available.
 - The event can be attributed to etiology other than the study drug or to factors unrelated to study conduct.
 - It becomes unlikely that any additional information can be obtained (patient or health care practitioner refusal to provide additional information, lost to follow-up after demonstration of due diligence with follow-up efforts).
- Any event requiring hospitalization (or prolongation of hospitalization) that occurs during the study must be reported as a SAE, except hospitalizations for the following:

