5.2 Safety Endpoints

5.2.1 Adverse Events

Safety will primarily be addressed by evaluations of the adverse events (AEs). AE is defined as any untoward medical occurrence in a patient or clinical trial patient associated with use of a drug in humans, whether or not considered drug related. An AE can be

- any unfavorable and unintended sign (including an abnormal laboratory finding, for example), symptom, or disease temporally associated with the use of a medicinal product, whether or not considered related to the medicinal product.
- any occurrence that is new in onset or aggravated in severity or frequency from baseline condition, or abnormal results of diagnostic procedures, including laboratory test abnormalities.

All AEs whether serious or non-serious, will be reported from the time a signed and dated informed consent form (ICF) is obtained until 30 days following the last dose of study drug or until the start of a subsequent systemic anti-cancer therapy, if earlier. AEs will be coded using the latest version of Medical Dictionary for Regulatory Activities (MedDRA). An assessment of severity grade will be made using NCI-CTCAE v5.0.

Both protocol-related AEs and serious adverse events (SAEs) will be collected from the time the patient has consented to study participation. AEs and SAEs reported between the time the patient signs the ICF and the administration of the first dose of study drug will be captured as concurrent medical history unless the events are attributed to protocol-specified procedures. Events attributed to protocol-specified procedures will be collected on the Adverse Event eCRFs and SAE Report form as appropriate.

Only treatment emergent adverse events (TEAEs) will be summarized as safety endpoints. A TEAE is defined as any event that is newly occurring on or after the administration of study drug or an event that existed before but increased in severity on or after study drug administration.

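### AE collection closes 30 days after the last dose, but the End of Treatment Visit is timed from the decision to stop, so new non-serious AEs arising between the two need not be collected

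*Protocol*

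**What the plan says.** **AE window.** Protocol 12.2.1 covers serious and non-serious AEs from consent "until 30 days following the last dose of study drug or until the start of a subsequent systemic anticancer therapy, if earlier". The opening of Protocol section 12 gives the safety assessment the same end, and SAP 5.2.1 repeats it.

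**EOTV.** Protocol 9.12 uses a different starting point: "The end of treatment visit (EOTV) should be performed within 30 days after the patient has met study treatment discontinuation criteria". It adds that the visit should come before any subsequent anticancer therapy, and that a missed EOTV is not a deviation.

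**Dose holds.** Protocol 4.3.1 states: "A dose delay of up to 20 days is allowed for patients experiencing AEs". Patients delayed longer than that must discontinue and then complete the EOTV.

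**Late SAEs.** Protocol 12.2.2 makes three statements about related SAEs.
- The opening paragraph says "SAEs considered related to study drug may be reported at any time, even after the" final visit.
- A bullet says "SAEs related to study drug may be reported at any time, through 30 days after the last dose of study drug", or until new anticancer therapy if earlier.
- A further bullet asks the investigator to report a suspected related SAE learned of after day 30.

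**TEAEs.** SAP 5.2.1 reads: "A TEAE is defined as any event that is newly occurring on or after the administration of study drug", or that worsened from then on. No end is given. SAP 6.8.1 summarizes TEAEs only.

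**Concomitant medications.** Protocol 9.5 covers those "administered for 30 days prior to study drug administration through the End of Treatment Visit must be recorded". Protocol 8.1 instead ends at 30 days after the last dose, or at new systemic therapy.

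**The concern.** The two clocks start on different days. The AE clock starts at the last dose and the EOTV clock at the decision to stop, so the last scheduled on-site safety visit can take place after AE reporting has ended. A site that finds a new Grade 2 immune-related event at a day-60 EOTV cannot tell from the text whether to record it. A programmer who receives it cannot tell from the SAP whether the TEAE period is still open.

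Safety and tolerability are part of the primary objective of the Tebotelimab Cohort (Protocol 3.1, SAP 2.1). The patients whose EOTV can fall latest are those whose dosing was held before it was stopped. The protocol foresees this course: its DLT list (4.2.2) includes an intolerable Grade 2 toxicity that interrupts dosing for more than 20 days.

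**Working it through.** The plan states no EOTV day relative to the last dose, so there is no figure to reproduce. The latest day follows from the stated windows.

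**Inputs** (day 0 = last dose)
- AE close: day 30 (Protocol 12, 12.2.1; SAP 5.2.1).
- EOTV: within 30 days after criteria are met (Protocol 9.12; Appendix 1, footnote b).
- Cycle: 21 ± 3 days (Appendix 1, footnote a).
- Permitted hold: up to 20 days; a longer one forces discontinuation (Protocol 4.3.1).
- Counting of delays: Protocol 7.1.2 equates a delay over 11 days with more than 35 days since the last dose. Since 24 + 11 = 35 (and 21 + 11 = 32), that rule counts the delay from day 24.

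**Formula.** If criteria are met on day m, the latest EOTV is day m + 30. It then falls (m + 30) − 30 = m days after AE close.

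| Situation | m | Latest EOTV | Days past AE close |
|---|---|---|---|
| Stopped soon after a dose, e.g. day 5 | 5 | 35 | 5 |
| Stopped at the next scheduled dose | 21 | 51 | 21 |
| Same, at the +3-day limit | 24 | 54 | 24 |
| After a 20-day hold | 21 + 20 = 41 | 71 | 41 |
| First day of a delay over 20 days | 21 + 21 = 42 | 72 | 42 |
| 20-day hold counted from day 24 | 24 + 20 = 44 | 74 | 44 |
| Delay over 20 days counted from day 24 | 24 + 21 = 45 | 75 | 45 |

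**The case that needs no assumption about visit timing.** Under the over-20-day rule, m is 42 to 45. AE collection closed 42 − 30 = 12 to 45 − 30 = 15 days before the criteria were met. Even counting from the shortest interval, m = 18 + 21 = 39, which is past day 30. Any EOTV in these patients therefore falls outside the AE window.

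**What still has a route after day 30**

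| Event | Text | Route |
|---|---|---|
| AE that causes discontinuation | Protocol 12.2.4.4: reported within 24 hours of stopping, followed to resolution or stabilization | Yes |
| SAE suspected to be related | Protocol 12.2.2: two statements allow it, one bullet caps it | Yes, but contradicted |
| SAE not suspected to be related | 12.2.2 asks for all SAEs during the study; 12.2.1 closes serious AEs at day 30 | Unclear |
| New non-serious AE, including an immune-related AESI, not causing the stop | 12.2.1 is closed; Table 5 sets a deadline from site awareness but no collection period | None required |
| EOTV laboratory tests, vital signs, examination | Appendix 1; laboratory values summarized by visit (SAP 6.8.2) | Yes, as measurements |

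**Concomitant medications.** With an EOTV on day 51, 9.5 runs 51 − 30 = 21 days longer than 8.1. With an EOTV on day 25, it ends 30 − 25 = 5 days sooner. Neither section refers to the other. Protocol 7.2.3 and 7.2.5 mention four-week steroid tapers; one begun on day 10 would end on day 10 + 28 = 38, after the 8.1 cut-off.

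**The case against.** A reader might infer that late toxicity in patients stopped for toxicity drops out of the safety data. The documents do not support that. Protocol 12.2.4.4 captures the AE that led to the stop and follows it with no 30-day limit. A toxicity that causes a hold must have begun by the missed dose, around day 18–24, so its onset lies inside the window. SAEs suspected to be related remain reportable after day 30 under two of the three statements in 12.2.2.

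Three other points against the concern also stand.
- The new-therapy cut-off should not come before the EOTV, because 9.12 places the visit before new therapy. That rule also tends to bring visits forward.
- The open-ended TEAE definition does not conflict with late SAE reporting. A related SAE reported at day 60 satisfies it. What is missing is a stated end to the period.
- Many toxicity stops are immediate, and the gap is then short. The documents give no distribution of EOTV days, so the share of patients affected cannot be calculated.

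The Adverse Events row of Appendix 1 has lost its column marks in the copy reviewed and is not evidence either way.

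None of this gives a collection route to a new-onset non-serious AE between day 30 and a later EOTV, or settles the differing windows.

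**Conclusion.** The point holds in a limited form. The EOTV can fall up to 21–24 days after AE close without a hold, and about 41–45 days after a maximum hold. These are latest dates under the protocol's windows, not typical ones, and the range reflects whether the delay is counted from day 21 or day 24. For every patient stopped under the over-20-day delay rule, AE collection has ended before the criteria for stopping are met.

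The events not required to be collected in that interval are new-onset non-serious AEs that did not cause discontinuation, including immune-related events of special interest. SAEs not suspected to be related have no clear rule. Separately, the cap in 12.2.2 contradicts the two statements allowing later related SAEs, and 8.1 and 9.5 give different ends for concomitant medications. The number of events affected cannot be estimated from the documents. This is a worthwhile, inexpensive improvement to the safety data, not a failure of the safety analysis.

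**What to change.** 1. In Protocol 12.2.1 and SAP 5.2.1, collect AEs to the later of 30 days after the last dose and the EOTV, still ending at the start of new systemic anticancer therapy. Where no EOTV takes place, day 30 applies. Carry the same wording into the opening of section 12 and the synopsis.
2. In Protocol 12.2.2, reconcile the bullet that caps related SAEs with the two statements that allow later reporting, and say what applies to SAEs not suspected to be related.
3. Give Protocol 8.1 and 9.5 one end date for concomitant medications, preferably that of the AE window.
4. In SAP 5.2.1, state the end of the TEAE period, and that later related SAEs are included in the tables and flagged.

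**Cost.** Wording changes in both documents, with AEs recorded at a visit that already exists. No dosing rule or endpoint changes. The AE window will vary somewhat between patients and incidence may read slightly higher; a tabulation restricted to 30 days after the last dose can be kept alongside for comparability.
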